#### ( 3 ) Immune enhancement

## **IX.Evaluation of adverse events**

1.Definition of adverse events : Any disease that occurs during a drug clinical trial, new symptoms, signs or abnormal laboratory tests, or deterioration of the original symptoms and signs, whether or not related to the test drug, is an adverse event.

---

2. Relationship between adverse reactions and experimental drugs : Searching through the CNKI database, no side effects and related adverse reactions of Ganoderma lucidum were found in the current study. If complained of discomfort, through laboratory tests such as blood routine, liver and kidney function, platelets, hemoglobin, determine or determine whether it is related to the test drug.

3. Adverse event recording and reporting channels :

In the event of adverse events, the occurrence time, clinical manifestations, treatment process and duration, outcome and the relationship between the test drugs should be recorded in detail on the case report form page. Serious adverse events should fill in the serious adverse events form and report to SFDA Registry Drug Research and Supervision Office within 24 hours, notify the team leader unit and the bidder, and report to the center ethics committee, and submit details within 7 days thereafter.

Safety evaluation at the end of the trial should include all patients who have used the test drug, regardless of whether they meet the evaluable criteria.

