## **VII.research process**

### 7.1 Screening / Baseline ( Week 0 )

- ( 1 ) Sign informed consent ;
- ( 2 ) Complete the verification of inclusion and exclusion criteria ;
- ( 3 ) to obtain demographic data and medical history data ;
- ( 4 ) Psychiatric examination and HAMD-24 scale evaluation ;
- ( 5 ) PSQI scale evaluation ;
- ( 6 ) Stool specimen collection ;
- ( 7 ) Thyroid function test residual blood collection ;
- ( 8 ) Women of childbearing age to do urine pregnancy test ;
- ( 9 ) Record the combined medication ;
- ( 10 ) Drug distribution.

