## **X. Statistical analysis of test data**

### **1. Data Selection for Statistical Analysis**

( 1 ) Full Analysis Set ( FAS ) : Constituted of all cases with depressive symptoms after papillary thyroid carcinoma surgery that were randomized into groups and at least 1 month after surgery, that is, Intention-to-treat. The FAS set was used for efficacy analysis, and the missing data was filled with the last observed data filling ( LOCF ) criterion.

( 2 ) Per-Protocol Set ( PPS ) : PPS is composed of all cases that meet the test plan, have good compliance, do not use prohibited drugs during the test, and complete the content of CRF requirements. The PPS set is used for efficacy analysis.

( 3 ) Safety Analysis Set ( SAS ) : It is composed of all cases that have been randomly grouped, used at least one drug and have safety evaluation. The SAS set is used for safety analysis.

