### **2. statistical analysis plan**

---

Statistical analysis was performed using SPSS 9.1.3 statistical software.

( 1 ) Distribution of two groups of cases : the comparison of the shedding and elimination rates of the two groups was performed by  $\chi^2$  test or exact probability method.

( 2 ) Comparability analysis : Demographic data and other basic indicators were compared to measure the comparability of the two groups. According to the type and distribution of data,  $\chi^2$  test or exact probability method, CMH test, t test, variance analysis or non-parametric statistical method were used.

( 3 ) Compliance analysis : To compare whether the two groups of patients use the test drugs on time and in quantity. The drugs that were not banned in the regimen were mainly tested by  $\chi^2$  test or exact probability method.

( 4 ) Validity analysis : Repeated measures were used to compare the differences in measurement data such as depression scores and sleep scores between the experimental group and the control group, or linear regression models were used to control baseline depression scores or sleep scores. Differences in depression scores and sleep scores between the two groups. Compare the score after the end of the experiment with the baseline score, calculate the difference before and after the change, and use the t test to compare the difference between the score changes of the experimental group and the control group.

( 5 ) Safety analysis : adverse reactions were statistically described, and the incidence of adverse reactions in the two groups was compared by  $\chi^2$  test or exact probability method.

( 6 ) All statistical tests should give test statistics and corresponding p values. When using the exact probability method, the p value is given directly.  $P \leq 0.05$  indicated that the difference was statistically significant.

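### Laboratory tests are the only stated basis for calling a complaint drug-related, and, read literally, only drug-related reactions are compared between arms

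*Combined protocol and SAP*

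**What the plan says.** Section IX, item 1 defines adverse events regardless of cause: any new or worsened finding, "whether or not related to the test drug, is an adverse event".

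Item 2 turns to relatedness. It reports a literature search in which "no side effects and related adverse reactions of Ganoderma lucidum were found in the current study", and then gives its method for linking a complaint to study medication: "If complained of discomfort, through laboratory tests such as blood routine, liver and kidney function, platelets, hemoglobin, determine or determine whether it is related to" … It names no other criterion, no causality scale and no assessor.

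Item 3 lists what goes on the case report form: "the occurrence time, clinical manifestations, treatment process and duration, outcome and the relationship between the test drugs should be recorded in detail". Timing, outcome and relationship are thus all recorded, but nothing says that the first two inform the third.

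In section X.2(5), "adverse reactions were statistically described, and the incidence of adverse reactions in the two groups was compared by" a chi-square or exact test. No between-arm comparison of all adverse events is written. The population is fixed in section X.1(3): "The SAS set is used for safety analysis".

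The only blood work scheduled in section VII is "Thyroid function test residual blood collection", at baseline and again at day 90.

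**The concern.** The trigger in item 2 is a complaint of discomfort, which is a symptom. The evidence then called for is a laboratory work-up. The named tests are useful when the event involves blood, liver or kidney. They say little about a complaint such as stomach upset, rash or poor sleep, where the results may be normal whether or not the powder is the cause. With no scheduled baseline panel, an out-of-range value found after a complaint may also have been there before treatment.

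The weakness matters because of what follows it. If section X.2(5) means what it says, an event reaches the between-arm test only after it has been judged related. A real excess of symptomatic reactions on the powder could be recorded correctly on the form and still not appear in the comparison. The trial would then report no difference in safety on incomplete evidence. The literature search found no known reactions, so there is no list of expected reactions to guide attribution, and the item 2 method carries the whole decision.

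**Working it through.** **The path of an event**

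1. A symptom occurs and counts as an adverse event whatever its cause (IX, item 1).
2. It is recorded with timing, course, outcome and relationship (IX, item 3).
3. The relationship is settled through laboratory tests (IX, item 2). The list is given as examples, but they are examples of laboratory tests. Onset relative to dosing and alternative causes are not laboratory tests, so the open list does not bring them in.
4. Adverse reactions are compared between arms (X.2(5)).

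Step 3 therefore stands between the recorded events and the only safety test.

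**What can be calculated**

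The plan gives no adverse event rate, no attribution accuracy and no power for safety. The sample size in section 5.1 rests on a regulatory minimum and 15% dropout. There is no safety figure to reproduce, and what follows is illustration only.

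- From the plan: 200 patients on powder and 100 on placebo (5.1); significance at 0.05 (X.2(6)). Two-sided testing is assumed, since sidedness is not stated.
- Assumed: background rate b on placebo and total rate t on powder.
- Assumed: a share s of the excess events and a share f of the background events is called related.
- Rates compared: placebo f × b; powder f × b + s × (t − b).
- Power: binomial probabilities summed over all tables in which the pooled chi-square, without continuity correction, is significant.

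When s = f, attribution carries no information. When s > f, it is informative. When s < f, drug-caused symptoms are missed more often than background events are excluded correctly.

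| Events compared | 5% v 20% | 5% v 15% | 10% v 20% |
|---|---|---|---|
| All adverse events | 97% | 77% | 61% |
| s = f = 0.65 | 83% | 53% | 39% |
| s = f = 0.50 | 70% | 40% | 29% |
| s = f = 0.30 | 43% | 22% | 17% |
| s = 0.8, f = 0.2 | 99% | 88% | 78% |
| s = 0.6, f = 0.3 | 89% | 63% | 49% |
| s = 0.1, f = 0.3 | 7% | 4% | 5% |

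Example for 5% v 20%:

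- s = f = 0.50: placebo 0.5 × 5% = 2.5%; powder 2.5% + 0.5 × 15% = 10%. The 15-point difference shrinks to 7.5 points.
- s = 0.8, f = 0.2: placebo 1%; powder 1% + 12% = 13%.
- s = 0.1, f = 0.3: placebo 1.5%; powder 1.5% + 1.5% = 3%.

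For the sparse rows the plan's exact-test option could apply in place of chi-square.

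**Type I error**

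With equal true rates and sorting that is blind to arm, the compared rates stay equal. Exact type I error at common rates of 20%, 10% and 5% is 0.050, 0.049 and 0.047.

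**The case against.** **The text is underspecified rather than a closed rule.** A reader might infer that a normal panel makes an event unrelated and that any abnormal value makes it related. Item 2 says neither. This stands. What remains is that laboratory testing is the only basis named.

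**The tests are informative for some events.** A reader might go further and infer that the panel says almost nothing about cause, so that events are sorted largely by chance. The documents do not support this. The tests do inform on haematological, hepatic and renal events, and the plan gives no accuracy from which chance sorting could be derived. It is true that if 14, 20 or 25 analytes each had an independent 5% chance of being out of range, at least one would be so in 1 − 0.95^14 = 51%, 1 − 0.95^20 = 64% or 1 − 0.95^25 = 72% of patients without any drug effect. But the analyte counts and independence are assumptions, correlation lowers the figures, and the plan does not treat a trivial deviation as proof of relatedness.

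**Item 3 already records timing, outcome and relationship.** This is true, and nothing forbids an investigator from using them. But nothing directs it either, and other plausible causes are not on the list.

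**Adverse reactions may be loose wording for adverse events.** Section 4.4 gives the abbreviation SAE to severe adverse reactions, so the terms are not kept apart. If X.2(5) means adverse events, the filter disappears. This is a fair objection, and it is why the point is stated for the literal reading. The ambiguity itself needs settling.

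**Filtering need not cost power.** Good attribution can raise it, as the row s = 0.8, f = 0.2 shows. This stands, and it argues for stating sound criteria.

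**Conclusion.** The point holds in a limited form. Laboratory tests are the only stated basis for relatedness. They are weak for symptoms without a laboratory sign, no baseline panel is scheduled, and on a literal reading the decision filters the only between-arm safety comparison. A real excess of symptomatic reactions may be hidden.

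No single size can be given. In the illustration, power after filtering runs from far below to slightly above that for all events, according to accuracy that the plan does not state. All event rates and shares there are assumptions. What is at risk is sensitivity and an understated difference. False positives are not inflated, provided that attribution is blind to arm, as the double-blind design in section III implies. The plan should be changed because the remedy is cheap and the present text gives no assurance about accuracy.

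**What to change.** 1. **Section IX, item 2.** Replace the sentence on laboratory tests. The investigator, blind to treatment, judges relatedness from onset relative to dosing, course and outcome (already recorded under item 3) and other plausible causes. Laboratory results are supporting evidence only, and a normal panel is not sufficient to call an event unrelated.
2. **Adverse event page.** Add a field for other plausible causes. The relationship is already recorded there.
3. **Section X.2(5).** State that all adverse events in the safety analysis set are compared by arm, with related events as a secondary comparison.

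The third change is the one that takes the main comparison out of reach of the attribution step. The first improves only the secondary comparison and would not by itself give the all-events power in the table.

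The cost is a few sentences and one field, with no new test or visit. The downsides are slightly more recording and, probably, more events reported as related.

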## **X. Statistical analysis of test data**

### **1. Data Selection for Statistical Analysis**

( 1 ) Full Analysis Set ( FAS ) : Constituted of all cases with depressive symptoms after papillary thyroid carcinoma surgery that were randomized into groups and at least 1 month after surgery, that is, Intention-to-treat. The FAS set was used for efficacy analysis, and the missing data was filled with the last observed data filling ( LOCF ) criterion.

( 2 ) Per-Protocol Set ( PPS ) : PPS is composed of all cases that meet the test plan, have good compliance, do not use prohibited drugs during the test, and complete the content of CRF requirements. The PPS set is used for efficacy analysis.

( 3 ) Safety Analysis Set ( SAS ) : It is composed of all cases that have been randomly grouped, used at least one drug and have safety evaluation. The SAS set is used for safety analysis.

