## IV.case selection

### 4.1 inclusion criteria

- ( 1 ) Patients with depressive symptoms after papillary thyroid carcinoma surgery in the outpatient department of Zhejiang Cancer Hospital ( patients with depressive symptoms by clinical psychiatrist and Hamilton Depression Scale score of 8-20 points ) ;
- ( 2 ) Han nationality ;
- ( 3 ) no previous depression and other mental diseases ;
- ( 5 ) 18-80 years old ;
- ( 6 ) Women ;
- ( 8 ) BMI : 19 ~ 24. ( BMI calculation method :  $BMI = \text{weight ( kg )} / \text{height}^2$  ( m ) )

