### 4.2 excluded criteria

- ( 1 ) suffering from other diseases of the intestinal system ;
- ( 2 ) Have received gastrointestinal surgery before intervention ;
- ( 3 ) Including patients with other malignant tumors, who need chemotherapy, radiotherapy, biological therapy or traditional Chinese medicine treatment ;
- ( 4 ) received antibiotics or microecological modulators within 3 months before the intervention ;
- ( 5 ) Acute intestinal obstruction ;
- ( 6 ) Patients with severe depressive symptoms who must receive antidepressant treatment ;
- ( 7 ) organic diseases such as heart and brain diseases, brain trauma ;
- ( 8 ) history of mental illness, use of psychoactive drugs such as drugs ;
- ( 9 ) Severe liver and kidney dysfunction ;
- ( 10 ) Pregnancy, lactation

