### 4.3 rejecting standard

- ( 1 ) After enrollment, it was found that the included objects did not meet the inclusion criteria ;

---

( 2 ) Subjects who did not take oral ganoderma lucidum spore powder or intervene in the course of dissatisfaction after enrollment according to the study protocol ;

( 3 ) poor compliance, midway active withdrawal or lack of main indicators, incomplete data, etc., can not determine the efficacy or safety.

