### 5.3 medication regimen

(1) From the first day after enrollment, the subjects were given oral research drugs ( wall-removing spore powder / placebo ), once in the morning and once in the evening, 1 packet ( 2g ) each time, for 90 days. Taking method : 50ml warm boiled water into suspension.

(2) dosage adjustment: If this scheme has not been revised in writing, the dose of the test drug shall not be adjusted.

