#### ( 2 ) Validity standard

Depression relief : After 90 days of treatment, HAMD score decreased.

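### The Full Analysis Set carries an undated condition of one month after surgery that no visible eligibility rule contains, so it does not match its intention-to-treat label

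*Combined protocol and SAP*

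**What the plan says.** Section X.1 (1) limits the FAS to cases with depressive symptoms after papillary thyroid carcinoma surgery that were "randomized into groups and at least 1 month after surgery, that is, Intention-to-treat". It gives the set its purpose in the next sentence: "The FAS set was used for efficacy analysis, and the missing data was filled with the last observed data filling ( LOCF ) criterion". The leading indicator in section 8.1 is therefore covered: "Depression relief : After 90 days of treatment, HAMD score decreased".

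The entry rules contain no matching condition:

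- Section 4.1 (1) admits "Patients with depressive symptoms after papillary thyroid carcinoma surgery in the outpatient department of Zhejiang Cancer Hospital", with a Hamilton score of 8-20. It requires that surgery has taken place but not how long ago.
- Section 4.2 mentions surgery once, and it is a different operation: "Have received gastrointestinal surgery before intervention".
- Section 4.3 (1) rejects a case when "After enrollment, it was found that the included objects did not meet the inclusion criteria", which refers back to 4.1 and adds no interval. Section 4.4 adds none either.
- Section 7.1 (2) verifies the inclusion and exclusion criteria and lists no separate check of the surgery date.
- Section 5.3 ties treatment to enrolment and not to surgery: "From the first day after enrollment, the subjects were given oral research drugs".

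The other two analysis sets in X.1 do not carry the condition. The Per-Protocol Set (PPS) depends on adherence to the plan, no prohibited drugs and a complete CRF. Of the Safety Analysis Set the plan says: "It is composed of all cases that have been randomly grouped, used at least one drug and have safety evaluation".

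**The concern.** An intention-to-treat set contains everyone who was randomised. A set defined as randomised plus a further condition is something else, unless entry to the trial already guarantees that condition. Nothing in the visible text guarantees this one.

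This sentence decides whose HAMD-24 score counts in the FAS efficacy result, and the PSQI score as well. Because the clause has no anchor date, two analysts could apply it to the same data and obtain different sets, and the choice could be made after the data have been seen. On one reading the trial also treats patients whom its main efficacy set leaves out. On another it removes patients because of something that happened after randomisation.

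**Working it through.** **The plan's own figures.** Section 5.1 starts from 100 pairs and allows 15% shedding: 100 / (1 − 0.15) = 117.6. This rounds up to 118; the plan states 117, a difference of one pair that does not matter here. The final 300 at 2:1 gives 300 × 2/3 = 200 and 300 × 1/3 = 100. The control arm therefore starts at exactly 100, and any control left out of the FAS takes it below 100.

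**Reading 1: interval counted at enrolment.** Take a woman enrolled 2 weeks after surgery with a HAMD score of 12. She meets 4.1 (1) on interval and score and, if she meets the other criteria, is randomised and dosed from the first day. She is outside the FAS. If she complies and completes, she meets the PPS definition, and she is in the safety set. A per-protocol set that can contain patients absent from the full analysis set does not nest. Time since surgery at enrolment is fixed before allocation, so the restriction does not depend on arm. It reduces numbers and narrows the population.

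**Reading 2: one month on study.** This removes patients who leave before about D28 (Visit 1, section 7.2). Leaving early happens after randomisation and could differ between arms. These are also patients whom an intention-to-treat set exists to keep.

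**Reading 3: interval counted at assessment or analysis.** The same woman is 14 + 28 = 42 days (6 weeks) after surgery at Visit 1 and 14 + 90 = 104 days (about 15 weeks) at Visit 2. With the ±3 day window, Visit 1 can fall on D25. Taking a month as 30 days, only a patient enrolled fewer than 30 − 25 = 5 days after surgery could fall short at Visit 1, and none could at Visit 2. The clause then does almost nothing.

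**Size under reading 1.** The documents do not give the share s enrolled within a month of surgery, so s is an assumption that includes zero and is taken as equal in both arms. The formulas are:

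- FAS size = 300 × (1 − s); controls = 100 × (1 − s).
- Standard error relative to the full 300 = 1 / √(1 − s).
- Power = Φ(d × √(n₁n₂ / (n₁ + n₂)) − 1.96), with two-sided alpha 0.05 and 2:1 allocation.

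The plan gives no effect size, SD or power, and does not state the sidedness of its 0.05, so the standardised differences d = 0.35 and d = 0.5 are also assumptions. At s = 0 and d = 0.35: √(200 × 100 / 300) = 8.165; 0.35 × 8.165 − 1.96 = 0.898; Φ(0.898) = 81.5%.

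| Assumed s | FAS | Controls | Relative SE | Power, d = 0.35 | Power, d = 0.5 |
|---|---|---|---|---|---|
| 0% | 300 | 100 | 1.00 | 81.5% | 98.3% |
| 5% | 285 | 95 | 1.03 | 79.5% | 97.8% |
| 10% | 270 | 90 | 1.05 | 77.4% | 97.2% |
| 20% | 240 | 80 | 1.12 | 72.4% | 95.5% |
| 30% | 210 | 70 | 1.20 | 66.7% | 92.7% |

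The 15% shedding is not subtracted as well, because LOCF keeps many of those patients in the FAS.

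**The case against.** The best defence is that the clause may only restate the intended population. The inclusion list in 4.1 runs (1), (2), (3), (5), (6), (8). Items (4) and (7) are absent, and the technical-route figure in section III is not shown. If an interval criterion was meant to stand at entry, the FAS clause would drop no eligible patient. The phrase may also be a translation slip. This limits how firmly the point can be put: one can say that no visible rule contains the condition, not that the sponsor never had one. It does not rescue the text, because a reader cannot tell from it who is in the FAS.

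A reader might go further and infer three things that the documents do not support.

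- *That the clause biases the comparison of arms.* On the enrolment reading it cannot do so through allocation, because the interval is fixed beforehand. The possibility of bias belongs only to the time-on-study reading, and even there the documents do not show that early exit would differ by arm.
- *That HAMD-24 data from recently operated patients are thrown away.* X.1 (2) also uses the PPS for efficacy, so compliant completers are analysed there, and their safety data are kept.
- *That a known number of patients is lost.* No share is given. The range above is illustration only, and under the assessment or analysis reading, or with an intended entry rule, the loss is zero or close to it.

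**Conclusion.** The point stands as a defect of definition that should be fixed. X.1 (1) calls a set intention-to-treat while attaching a condition that no visible entry rule contains and that has no reference date. As worded it can leave eligible, randomised and treated patients out of the FAS, and it allows the PPS to include patients the FAS omits.

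The consequence depends on the reading: fewer patients and lower precision (interval at enrolment), a post-randomisation exclusion that could differ by arm (time on study), or almost nothing (interval at assessment or analysis). The size cannot be computed from the documents. Under the assumptions shown, a 10% loss would cost about 4 percentage points of power at d = 0.35 (81.5% to 77.4%) and about 1 point at d = 0.5 (98.3% to 97.2%). The case for correction rests on the contradiction and the ambiguity, not on those figures.

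**What to change.** Delete the one-month condition from X.1 (1), so that the FAS is all randomised patients analysed in the group to which they were randomised. This works on every reading and should be settled before unblinding.

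Ask the sponsor what the clause was meant to say. Only if a minimum interval since surgery was intended, reconcile X.1 (1) with 4.1 by stating it as an eligibility criterion, counted at the Week 0 visit and checked before randomisation under 7.1 (2). Adding such a rule without that confirmation would impose an entry restriction that the protocol may never have intended. Keep any patients already randomised who fall short of it in the FAS, say that 4.3 (1) does not remove them from it, and show the result without them as a sensitivity analysis.

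The cost is one deletion and, if needed, one eligibility line; in that case some patients would wait before screening. If the clause had meant time on study, the deletion brings back patients who left before Visit 1. Their only HAMD-24 score may be the baseline, so the plan should state how LOCF treats them.

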### **V.test scheme**

#### 5.1 Number of cases and distribution of cases

According to the ' Drug Registration Management Method ', the study sample should be no less than 100 pairs. It is assumed that the case shedding rate is 15 %, and the sample size is not less than 117 pairs. Finally, the sample size was determined to be 300 cases. In order to reduce the use of placebo in the control group, so that more patients benefit from treatment, the experimental group : the control group was assigned to 2 : 1, that is, 200 cases in the experimental group and 100 cases in the control group.

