### 8.2 secondary index

#### ( 1 ) Changes of intestinal microbial diversity and metabolites in patients

( 2 ) Remission of sleep status : After 90 days of treatment, the Pittsburgh Sleep Quality Index score decreased.

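### Missing FAS scores are filled by LOCF alone, with no sensitivity analysis, so the D90 HAMD-24 and PSQI differences can be biased if scores change after the last visit attended

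*Combined protocol and SAP*

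**What the plan says.** Section X.1(1) defines the FAS as randomised patients at least one month after surgery, equates it with intention-to-treat, uses it for efficacy and adds that "the missing data was filled with the last observed data filling ( LOCF ) criterion". It requires no post-baseline score. No other method for missing scores, and no sensitivity analysis, appears anywhere in the document.

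The surrounding text bears on this as follows:

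- **Visits.** Sections 7.1 to 7.3 schedule HAMD-24 and PSQI at week 0, D28 and D90 only.
- **Endpoints.** Both are set at 90 days: "After 90 days of treatment, HAMD score decreased" (section 8.1(2)) and "After 90 days of treatment, the Pittsburgh Sleep Quality Index score decreased" (section 8.2(2)).
- **Dropout.** Section 5.1: "It is assumed that the case shedding rate is 15" per cent, with no split by arm or visit.
- **Second efficacy set.** "The PPS set is used for efficacy analysis" (section X.1(2)). The per-protocol set (PPS) is limited to patients who "have good compliance, do not use prohibited drugs during the test, and complete the content of CRF requirements". Neither set is named primary.
- **Efficacy models.** Section X.2(4): "Repeated measures were used to compare the differences in measurement data such as depression scores and sleep scores", or baseline-adjusted regression, together with a t test on change. It does not say how any of these treats a missing score.
- **Dropout check.** Section X.2(1): "the comparison of the shedding and elimination rates of the two groups was performed by" a chi-square or exact test.
- **Who counts as missing.** Section 4.3(3) rejects patients who withdraw or lack the main indicators, and section XI.3 counts a patient as shed once the emergency envelope is opened. Neither says whether these patients stay in the FAS.

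**The concern.** Under LOCF, a patient who misses D90 contributes a score that is about 62 days old (from D28) or 90 days old (from baseline). If scores would have moved in that interval, the movement is set to zero. What matters for the treatment comparison is whether the lost movement is the same in both arms.

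- If both arms improve and more control patients leave, or they leave earlier, control improvement is understated and a benefit appears that the drug did not cause.
- If the experimental arm loses more patients, the sign reverses.
- If the drug effect grows between D28 and D90, LOCF shrinks it even when dropout is identical in the two arms.

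The primary endpoint and the PSQI endpoint are both exposed. The plan has no second analysis of the same patients by which a reader could judge how far the result depends on LOCF.

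**Working it through.** **Inputs from the document.** 200 experimental and 100 control patients and 15% overall dropout (section 5.1); visits at week 0, D28 and D90 (sections 7.1 to 7.3); significance at 0.05 (section X.2(6), sidedness not stated, taken as two-sided).

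**The plan's own dropout figure.** 100 / (1 − 0.15) = 117.6 pairs, against the stated minimum of 117. So the 15% is read as intended, apart from rounding.

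**Assumptions not in the document.** SD of change 5; mean falls d28 and d90 from baseline, equal in both arms unless stated; half of dropouts leave before D28; dropout unrelated to scores; baseline carried forward when no later score exists. The dropout splits below all keep 45 of 300 patients, or 15%, overall. Positive bias favours the experimental arm.

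**Formulas.** With p the dropout share of an arm and late the share leaving after D28:

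- arm mean fall under LOCF = (1 − p) × d90 + late × d28
- bias = experimental mean fall − control mean fall
- SE = 5 × √(1/200 + 1/100) = 0.612
- type I error = P(|Z + bias/SE| > 1.96)

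**No drug effect, fall of 2 at D28 and 5 at D90:**

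| Dropout, exp./control | Experimental | Control | Bias | Type I error | Shedding test p |
|---|---|---|---|---|---|
| 10% / 25% | 0.90×5 + 0.05×2 = 4.60 | 0.75×5 + 0.125×2 = 4.00 | +0.60 | 0.165 | 0.0006 |
| 12.5% / 20% | 0.875×5 + 0.0625×2 = 4.50 | 0.80×5 + 0.10×2 = 4.20 | +0.30 | 0.078 | 0.086 |
| 15% / 15% | 0.85×5 + 0.075×2 = 4.40 | 4.40 | 0 | 0.05 | 1.0 |
| 20% / 5% | 0.80×5 + 0.10×2 = 4.20 | 0.95×5 + 0.025×2 = 4.80 | −0.60 | 0.165 | 0.0006 |

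The shedding test is a chi-square without continuity correction; for example, 25/200 against 20/100 gives p = 0.086.

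**Range at 10% / 25%.** The result depends on the assumed falls (D28/D90):

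| Fall | Bias | Type I error |
|---|---|---|
| 0/0 | 0 | 0.05 |
| 2/2 | 0.15 | 0.057 |
| 4/5 | 0.45 | 0.114 |
| 2/5 | 0.60 | 0.165 |
| 0/6 | 0.90 | 0.31 by formula, about 0.29 by simulation |

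The simulated value in the last row is lower because mixing carried and observed scores widens the spread, which the formula ignores. At fall 2/5, an SD of 4 or 6 in place of 5 gives a type I error of 0.23 or 0.13.

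**Equal rates, different timing (15% / 15%, fall 2/5).** If two thirds of control dropouts and one third of experimental dropouts leave before D28, the means are 0.85×5 + 0.10×2 = 4.45 and 0.85×5 + 0.05×2 = 4.35. The bias is +0.10, with a simulated type I error of about 0.056.

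**Equal rates and timing, but higher scores leave more often in the control arm only** (log risk 0.7 per SD, SD 5 per visit, correlation 0.5). Simulated bias is 0.26 and type I error about 0.07.

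**Real effect that grows (1.0 at D28, 2.0 at D90; 15% / 15%, equal timing).** LOCF estimates 0.85×2.0 + 0.075×1.0 = 1.775, or about 1.78.

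**The alternative.** In simulation a mixed model on the observed scores has bias 0.01 and type I error 0.048 at 10% / 25%, and 0.02 and 0.045 in the control-only selection case. These cases favour the model, since dropout is either unrelated to scores or driven by observed ones.

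**The case against.** **Nothing in the document predicts unequal dropout.** The trial is double-blind and placebo-controlled, and one 15% figure covers both arms. With the same dropout pattern and no drug effect the bias is zero, and mild imbalance leaves type I error at about 0.05 to 0.06. The larger figures need a 10% / 25% split, which the shedding test would flag. This stands and limits the size of the concern. But that test compares rates only: it would miss 12.5% / 20% and any difference in timing, and it does not correct the estimate.

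**The PPS is already planned.** It is close to a completers' analysis. In simulations with no drug effect a completers' test kept type I error at 0.049 to 0.056, so the PPS may expose a LOCF artefact. That simulated test leaves out the PPS selection on compliance and prohibited drugs, and the PPS does not correct the FAS result. With no primary set named, the plan has no rule if the two disagree.

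**Repeated measures are already named.** Section X.2(4) does not say that the model uses unfilled data, and section X.1(1) fills the FAS. A repeated-measures model run on filled scores keeps the problem.

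**Stronger readings that a reader might infer.**

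- *The carried value is undefined, so even the sign is open.* If a D28 score were required, some timing patterns would reverse the bias. The FAS, however, is all randomised patients with no post-baseline requirement, so carrying baseline forward is the plain reading. One clarifying sentence is enough.
- *LOCF is valid only if scores stay constant.* That is too strong for the between-arm difference: the third row of the first table has changing scores and no bias.
- *LOCF will favour the product.* The document gives no dropout by arm, and the shrinkage of a growing effect runs against the product.

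**Conclusion.** The concern holds in a limited form. LOCF is the only missing-data rule for the FAS and no sensitivity analysis accompanies it. The D90 difference can be biased in either direction if scores change after the last visit attended and dropout differs by arm in rate, timing or relation to scores. An effect that grows after D28 is diluted even without such differences.

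The size cannot be computed from the document, which gives no SD, expected change, or dropout by arm or visit. On the assumed values, a bias of 0.3 to 0.6 points and a type I error of about 0.08 to 0.17 go with moderate to large imbalance; little or nothing goes with mild or no imbalance. Bias here means departure from the difference that would be seen had every randomised patient been scored at D90, a target that the plan does not itself define.

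This should be changed because a better analysis is cheap. It is not evidence that the planned result would be wrong.

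**What to change.** In section X.1(1), replace LOCF with a mixed model for repeated measures on the observed D28 and D90 HAMD-24 scores, adjusted for baseline, in all randomised patients. Keep patients with no post-baseline score by putting baseline in the outcome vector or by multiple imputation. Report the D90 difference with its 95% CI as the primary FAS result.

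Also:

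- treat the PPS, the change-score t test of section X.2(4) and any LOCF result as supportive, and if LOCF is kept, state that baseline is carried forward;
- apply the same approach to PSQI;
- add one delta-adjusted or reference-based sensitivity analysis;
- state that patients rejected under section 4.3 or counted as shed under section XI.3 stay in the FAS.

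The cost is SAP wording and slightly more analysis work. The D28 scores are already collected, so no visit or patient is added. The model relies on data being missing at random, which the sensitivity analysis is there to probe.
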